Known or predictable factors that may impair outcomes and interpretation of outcomes

A different therapy standard between participating centers and/or within the same center can lead to very variable outcomes between one patient and another, all other conditions being equal. This problem is tackled by indicating in detail the therapy to be followed depending on the type of lesion.

An incorrect recording of photographic images does not make it possible to determine the area of the lesion via software. This problem is tackled by providing precise instructions on the correct use of the tools available for the retrieval of images.

Discontinuity of patients can affect recovery times. Before recruiting a patient, the doctor ensures that the patient is available to go, with the required timing, to the clinic, for the scheduled visits. This fact is underlined several times when providing study information to the patient.

Interruption and withdrawal of subjects from the clinical trial

Patients who miss the visits for two consecutive weeks, before/until the 14th week, and the patients who miss the visits for one week, after the 14th week, will be reached by phone by the Principal Investigator to assess their availability to go on with the study; in the event that the patient does not intend to continue with the visits at the centre, they will be excluded from the study. Also, the patient who will turn out to be absent for more than half of the sessions will be excluded as well.

Following the resignation or withdrawal from the study by a patient, their data collection form will be identified, scanned and archived.

If a patient withdraws from the study, the Principal Investigator or his delegate records the event in the Patient Identification Register and on the Data Collection Form and stores all documentation.

Monitoring plan of the clinical investigation

To guarantee the conformity with ICH/GCP guidelines, the Clinical Research Coordinator (CRC) will be responsible for the study to be carried out in full observance of the Standard Operating Procedures, of the Protocol and other written instructions.

The main responsibilities of the CRC are to ensure adherence to the Protocol, to make sure that the data are accurately and fully registered and reported and to verify that the Informed Consent was obtained and registered for each subject before the beginning of the study.

The CRC will keep in touch and meet the Principal Investigator on a regular basis throughout the whole duration of the study. The CRC will be allowed to check the various documents (Data Collection Forms, CRF and other related documents containing original data) related to the study in order to verify the conformity with the Protocol and to ensure the accuracy of recorded data.

Quality assurance, control procedures, data management and record-keeping

All the information gathered during the Study will be considered strictly confidential. The patients' consent to the registration of personal data will be requested at the time of recruitment; nevertheless the data collection forms will contain the Identification Code of the patient and their date of birth only. In order to guarantee the correct traceability of all parties involved, the number of the Study and the naming of the Center will be included as well.

At the end of the Study, all data will be archived using the appropriate safety measures at the Coordinating Site for a minimum of ten years.

If a patient withdraws their consent to data processing, they will be immediately destroyed to ensure total confidentiality, in addition each investigator will keep a copy of the study's documentation for at least two years after its conclusion.

The Principal Investigator builds and is responsible for the updating and custody of the Patient Identification Register or Enrollment Register.

The Patient Identification Register includes personal data of patients who agreed to take part in the study, the identification number assigned to the patient, their illness, indication of the eventual exclusion from the recruitment with its justification and date of recruitment. The patient code is constituted by a three-digit number: the first one indicates the center's number, as stated in this protocol, and the other two are sequential numbers, starting from 01. Only the Principal Investigator and, at their discretion, the members of their team have knowledge of the identities of patients enrolled in the study.

Deviations from the clinical protocol

In the case of isolated deviations from the protocol, these are registered in the data collection form, which is provided with a space to record any variation or comment the doctor deems appropriate. In case, during the study, a modification to the protocol is deemed necessary, the investigator communicates this need to the sponsor, who convenes the investigator of the coordinator centre, the study coordinator and any other experts in the field, and discusses the proposed variations and, where appropriate, submits a request for amendment to the Ethics Committees to approve the changes deemed necessary.

Adverse Events

Despite all the information in our possession and physical characteristics and performances of the device that do not suggest the possible occurrence of and adverse event, this section of the Protocol takes into consideration the possibility that said event could take place.

An Adverse Event (AE) is any untoward change in the state of health, or side effect, or unexpected benefit that could occur in a patient involved in in a clinical study while they receive the treatment or within a given timeframe following the conclusion of the therapy, not necessarily related to said treatment or clinical experimentation. An AE can consist in any unfavourable and/or unexpected sign or symptoms (including abnormal results from laboratory testing) or a pathology temporarily associated with the use of a medicinal product (subject of the experimentation) or experimental device, that whether or not is related to that medicinal product or device.

The morbid condition of each patient will be monitored the whole time of the study. During each visit any sign manifested by the patient will be carefully observed, in fact, the subject will be encouraged to report any symptom with direct questions, such as: "How have you been feeling since our last visit?". They will also be prompted to spontaneously report any adverse events that occurred during the study.

Any significant clinical anomaly encountered over the course of the study will be monitored and observed until its normalisation, or until it will be clinically explainable.

Serious Adverse Events

L.U.C.E. Study Protocol version 3.0 (24/02/2020)

A Serious Adverse Event (SAE) is defined as any unfavourable medical occurrence that, at any dosage, will result in any of these consequences:

- Death of the patient
- Any inauspicious outcome in the short term
- Hospitalization or prolonged hospitalization of the subject
- Disability or significant/persistent incapacity
- Other major medical event

Other medical events that do not involve the death of the patient, or do not endanger their life, or do not require the hospitalization of the subject can be also classified as SAE when, according to proper medical assessment, they may constitute a risk for the subject or they may require medical intervention or surgery to prevent one of the outcomes previously described.

Hospitalization is defined as the eventuality in which the subject is withheld (usually for at least a night) in hospital or in the emergency room for observation and/or treatment. Whenever is questioned if the hospitalization took place or if it was necessary, the adverse event must be considered serious. It is not necessary to consider as an Adverse Event a hospitalization due to elective surgery or due to the implementation of routine clinical procedures that are not consequences of an Adverse Event. If during the procedure an unfavourable eventuality is reported, it shall be considered as an Adverse Event, if Serious or not it will be decided according to customary criteria.

Reporting of Adverse Events or Serious Adverse Events

All the Adverse Events reported by the subject or observed by the Ricercatore or by members of their teamwill be mentioned on the SAE form.For each Adverse Event

must be gathered the following information:

- Date and Time of insurgence and resolution (duration)
- Extent (further defined in the text)
- Treatment eventually requested or measures taken
- Outcome
- Relation with the product used in the experimentation (further defined in the text)
- If the Adverse Event caused the subject to withdraw from the study

All the Adverse Events must be registered using the accepted diagnosis, whenever possible. Any alteration of laboratory results, vital sign, or reported by the physical examination must not be registered as an Adverse Event if it is known that they constitute a symptom or a sign of a diagnosis already reported as it is. For example: an ST segment elevation detected by an EKG and an increase of creatine phosphokinase are both well known signs of myocardial infarction and it will not be necessary to report them if myocardial infarction is already registered ad an Adverse Event. However, if both of them happen separately and a myocardial infarction has not been diagnosed, this eventuality must be registered as an Adverse Event.

Severity Classes and causal relationship of Adverse Events must be defined using the following parameters:

Gravity:

- *Mild* easily tolerated, does not interfere with daily activities
- *Moderate* causes some interference with daily activities
- Severe all daily activities are completely compromised

Relationship with procedures required by the study:

- *Not correlated* temporal association among the Adverse Event and the use of the product results in an extremely unlikely association between the two.
- *Possibly correlated* the adverse event occurs with a timing compatible with the beginning of the use of the product employed in the study, but it is also attributable to the clinical condition of the patient or the procedures/condition of the study.
- Undoubtedly corelated the adverse event occurs with a timing compatible with the beginning of use of the product employed in the study, recedes with its discontinuation and re-emerges when its reintroduced.

In addition to registration in the Data Collection Form (AE), the Adverse Events considered serious (SAE) that comprehend Suspicious and Unexpected Adverse Reactions (SUSAR) must be reported by the ricercatore in the Serious Adverse Events Report Form. This last document must be compiled and sent immediately to the Clinical Research Coordinator of the study, namely withing twenty-four from the moment the research staff diagnosed an SAE.

Safety follow-up for subjects withdrawn from the study

The subjects that withdrew from the experimentation after the treatment with the device under study for any reason, will undergo a continued monitoring of the Adverse Events in place until the results from the tests related to the Adverse Event, and required by the SOC, will recover to baseline or until the investigator will determine that those events are not clinically relevant anymore. The subjects who present Adverse Events up until thirty days from the last visit or the last follow-up check (whichever of the two eventualities is the latter) will be monitored until their test results are not recovered to baseline, or until the investigator does not determine that the results are not clinically relevant.

Safety follow-up for subjects who have completed the study

All the subject who still present Adverse Events upon completion of the study will be monitored until the test results are not back to baseline, or is no longer expected from them to change, or until the investigator does not determine that those results are no longer clinically relevant.

Amendments to the clinical evaluation plan

If, during the study, a modification to the protocol is deemed necessary the investigator communicates this need to the sponsor, who convenes the investigator of the coordinator centre, the study director and any other experts in the field, and discusses the proposed variations and, where appropriate, submits a request for amendment to the Ethics Committees to approve the changes deemed necessary.

If a substantive amendment request is necessary, the clinical trial will be suspended until approval has been received by the relevant ethics committees.

Early termination and suspension of clinical evaluation

In the event of suspension or early termination of the study by the sponsor, taken as a safety measure due to events related to the conduct of the study that may affect the health of the patients recruited, the promoter is required to notify the Ministry of Health and the Ethics Committees involved within 90 days from the recruitment of the last patient or the early closure. In case of suspension or early termination of the study not for safety reasons, the sponsor shall justify and explain their decision. The suspended clinical trial cannot be reactivated unless a substantive amendment and the positive opinion of the Ministry of Health and the Ethics Committees have been submitted.

Statistics

Calculation of the sample size

80 patients will be recruited during the study; they will be randomized 1:1 to the standard treatment group and the EmoLED Protocol group. In the control group, which follows the standard treatment, patients will be visited twice a week. The EmoLED experimental Protocol group will undergo medical examination once a week; in this case, therapy will consist in the standard treatment plus EmoLED treatment.

This sample size is sufficient to compare the average rate of the injured area reduction, considering Student-T test for the comparison between independent samples, by establishing $\alpha = 0.05$, power level (1- β) = 0,8, under the assumption to have an area reduction rate after 16 weeks amounting to 50% in Group 1 (control group), a difference of 20% between Group 2 (experimental group) and Group 1, a standard deviation of averages equal to 50% of the mean values and a bilateral hypothesis.

Statistical analysis

The average rate of reduction of the injured area between the two groups will be compared using the Student-T-test, the quality of life in both groups at the baseline, after 16 weeks and the difference with the baseline will be compared using Student-T-test for independent samples.

Linear regression models will be used to value the differences between the groups to exclude any confounding factors. Due to the usually asymmetrical nature of cost distribution, the comparison of the costs related to the treatment and control group, in both the NHS and society perspective, will be made using the non-parametric Mann-Whitney U test.

Generalized linear regression models will be used to value the differences between the groups to eliminate any confounding factors.

The cost-effectiveness of both treatments in the time frame of the study (16 weeks) will be valued by calculating the incremental cost-effectiveness ratio (ICER) and expressed in terms of incremental costs for "quality adjusted years (QALY).

Extrapolations of results about the cost-effectiveness that simulate longer time-frames will be made considering decision-making models (e.g. Markov models) and eventually including the data gathered during the study with literary data and/or evidence from other studies.

Data publication policy

L.U.C.E. Study Protocol version 3.0 (24/02/2020)

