The parameters of the Data Collection Form are acquired and kept on paper for the clinical trial lenght, and conserved in both paper and digital form; the pictures of the lesion are acquired and kept in digital form, during the length of the clinical trial and afterwards.

During each visit, a picture of the lesion will be taken so that the process of healing can be valued also in a visual way. Each picture will be named with the patient code and the date of the visit. In case of multiple lesions matching with both inclusion and exclusion criteria, they will be all treated following the same protocol, depending on the group of treatment, but only the lesion with the wider area will be registered; to distinguish the area of interest, the perilesional tissue will be labelled with single-use permanent markers.

Data Collection Form

The Data Collection Form is unique for each patient and includes: Clinical Section, Quality Life Section and Economic Section. The Clinical Section contains identification code of the patient, date of birth, sex, etiology of the ulcer, any eventual concurrent disease, any drug therapy (in terms of active substances), ulcer's date of onset, date of entry to the facility.

The second part of the form is organized as a matrix where the row represents the measurable parameters for each time of observation (reported in column).

The investigator marks with an "X" the chosen value for each parameter and the most suitable description. The Principal Investigator will also fill a check list, for each visit, to ensure that also the pain level has been measured and that the picture of the lesion has been taken.

There is also a "Notes" section to register information not planned at first, that might be helpful during the data analysis.

The last part of the Data Collection Form is about follow-up visit (after 4 weeks).

The Data Collection Form is already completed with the patient's recruitment code and the group they belong to, so that the allocation to the EmoLED group and the control group is random. The allocation sequence of the group is generated by Matlab.

On each visit, the patient will be asked to rate their current pain level (VAS scale 0-10).

The quality section survey will be administered on the first and last visits, and also every 4 weeks. In detail, standard questionnaires as the EQ-5D2 and the Wound-Qol3 will be administered, both available and validated in Italian language.

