Specific questionnaires for recognition of costs (Economic section) will be administered to patients and their primary caregiver (if present) during the first visit, with the aim of identifying the resources absorbed by the patients (and their caregivers) treated in the two different approaches. The consumption of resources will be measured by gathering information about the quantification of direct health costs (visits, hospitalizations, emergency healthcare, medications etc...), direct non-health-related costs (informal medical assistance, transportation and accommodation costs for each visit etc...) and indirect costs (productivity loss for both the patient and the caregiver/s) and also by taking into account both the costs associated with the adherence to the treatment, taking the first visit as a reference parameter, and the costs related to complications and events associated with the ulcer that determined the need for treatments/ exams and/or medical evaluations. The Principal Investigator will be given also a questionnaire to determine the costs incurred by their facility for handling patients with leg ulcers.

The questionnaires meant to value customer satisfaction, complexity and helpfulness of EmoLED device will be administered to doctors and to healthcare personnel involved in the treatment at the end of the trial.

Image Acquisition

For the 16 weeks of the trial, during each visit a picture of the lesion will be taken, so that the process of healing can be valued also in a visual way. Each picture will be named with the patient code and the date of the visit. The quantitative analysis about the size of the lesions through the collected pictures will be performed at certain time points: at the beginning, in the middle and at the end of the treatment.

The image analysis is made through an appropriate analysis algorithm that measures the area of the lesion (mm²). The lesion must be fully and frontally framed to obtain an optimal analysis. The ruler with patient's ID code and date must appear in every picture. It is important that the ruler is placed straight and in-focus to have the scale reference. If there is a wide lesion that needs more than one picture it's advisable to

L.U.C.E. Study Protocol version 3.0 (24/02/2020)

locate several markers around the lesion and take photos of adjacent areas, including at least two visible markers of the previous picture, to have the complete image of the lesion through a sequential photo array.

Bias

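### The patient and caregiver cost questionnaire is scheduled only at the first visit, so routine between-visit resource use over the 16 weeks has no stated measurement for the cost comparison and the ICER

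*Combined protocol and SAP*

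**What the plan says.** The Data Collection Form section gives the patient and caregiver cost instrument one time point: "Specific questionnaires for recognition of costs (Economic section) will be administered to patients and their primary caregiver (if present) during the first visit". The stated purpose is "with the aim of identifying the resources absorbed by the patients (and their caregivers) treated in the two different approaches". The scope is wide. It covers direct health costs, direct non-health costs such as informal help and transport, and "indirect costs (productivity loss for both the patient and the caregiver/s"). Costs of adhering to treatment are to be reckoned "taking the first visit as a reference parameter". Also to be counted are "the costs related to complications and events associated with the ulcer", with no form or time point named. For the sites, "The Principal Investigator will be given also a questionnaire to determine the costs incurred by their facility", again without a time point.

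Other instruments in the same section do have later time points. For quality of life: "The quality section survey will be administered on the first and last visits, and also every 4 weeks". Pain is rated at each visit. The staff questionnaires on satisfaction and usefulness of the device "will be administered to doctors and to healthcare personnel involved in the treatment at the end of the trial".

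Measurable parameters lists an economic survey without a schedule. Registration of clinical data says in general terms that endpoint data come from the visits in both groups. Secondary endpoints 4 and 7 are costs (health-service and societal perspectives) and cost-effectiveness. Statistical analysis plans a Mann-Whitney test on costs, generalised linear models, a 16-week ICER per QALY, and extrapolation to longer horizons, for example by Markov models.

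**The concern.** At the first visit a Group 2 patient has not yet lived under the once-weekly regimen. A questionnaire given then can describe past resource use and the cost of one attendance. It cannot show how the two regimens differ in use between visits over the following 16 weeks.

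That difference matters here because the experimental arm combines a device with half the planned visits. The obvious economic question is whether some care moves from the clinic to the home, to a community provider or to a caregiver. The opposite question is just as relevant: if ulcers heal faster with EmoLED, informal care and lost work should fall, and that benefit would also be missed.

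At stake are secondary endpoints 4 and 7, the 16-week ICER, and any longer-term model built on them. Economic impact is also a stated purpose of the study in the rationale section.

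**Working it through.** **1. Planned visits, reproduced.** Group 1: 16 weeks × 2 = 32. Group 2: 16 × 1 = 16. Both agree with Measurable parameters.

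**2. Scheduled administrations.** Patient and caregiver cost questionnaire: 1 (first visit). Quality-of-life section over a full 16 weeks: about 5 (first visit, weeks 4, 8 and 12, last visit).

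**3. What each stated source can supply after randomisation.**

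| Source | Supplies | Does not state that it covers |
|---|---|---|
| Attended visits × a first-visit unit cost | Clinic attendance, transport, time lost to attend | Use between visits |
| Complication and ulcer-event costs; adverse event records | Events needing treatment, tests or medical evaluation | Routine care that is not an event |
| Facility questionnaire | Site costs | Patient and caregiver costs |
| Notes and deviation records | Whatever the doctor chooses to write | A question put to every patient |
| General statement that endpoint data come from visits | An intention | Any schedule for the Economic section |

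What is left is routine between-visit use: dressing changes outside study visits, purchased dressings, informal care and lost work not tied to attending.

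**4. Illustrative size.** The documents give no unit cost or rate, so every input except the visit counts is an assumption.

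- c = cost of a standard visit.
- d = extra cost of an EmoLED application, as a share of c.
- m = between-visit use in Group 2 net of Group 1, in visit-equivalents over 16 weeks. It may be positive, zero or negative.

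If clinic visits are the whole counted cost base and all planned visits are attended:

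- Counted saving = 1 − 16(1 + d)/32
- True saving = 1 − [16(1 + d) + m]/32
- Error = m/32, whatever d is; one unit = 1/32 = 3.1 percentage points

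| d | Counted (m = 0) | m = −2 | m = 1 | m = 2 | m = 4 |
|---|---|---|---|---|---|
| 0 | 50.0% | 56.3% | 46.9% | 43.8% | 37.5% |
| 0.1 | 45.0% | 51.3% | 41.9% | 38.8% | 32.5% |
| 0.2 | 40.0% | 46.3% | 36.9% | 33.8% | 27.5% |

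Here m = 2 is one extra visit-equivalent per 8 weeks and m = 4 is one per 4 weeks.

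**5. Wider cost base.** If visits are half of Group 1 cost, the Group 1 total is 64c and one unit is 1/64 = 1.6 points. With d = 0.1 and the other 32c equal in both arms, the counted saving is 1 − (17.6 + 32)/64 = 22.5%. It becomes 19.4% at m = 2 and 25.6% at m = −2.

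**6. Sign.** With visits as the whole base, the counted saving vanishes only when 16(1 + d) + m = 32. At d = 0.1 that is m = 14.4, or 0.9 per week. Small shifts change the size of the saving, not its sign.

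**7. ICER.** Uncounted use adds m × c to the incremental cost, so the ICER moves by m × c divided by the incremental QALYs. Neither c nor the QALY difference is given, so this cannot be sized.

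**The case against.** The best defence is that the protocol never says the questionnaire is given only once. Several statements point past the first visit:

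- Endpoint data are said in general to be acquired during the visits.
- Complications and ulcer events under treatment cannot be known at the first visit, so counting them implies later collection.
- Using the first visit as reference plausibly means a unit cost multiplied by attended visits, which is enough for travel and for work lost to attend.
- The Economic section belongs to a form that also has a per-visit matrix. The form is not in the documents and may hold later cost items.
- Patients are asked at each visit how they have been since the last one. An extra dressing change prompted by deterioration may count as an ulcer event or be recorded as a deviation.
- Each visit ends with a foam dressing and compression bandage, and nothing provides for changes at home. Net between-visit use may be small or zero.

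Most of this stands, and it narrows the point to routine use that is not an event. It does not remove it. The general statement sets no economic schedule, while the one specific statement names the first visit. Site staff following the text would have no instruction to ask again.

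Two stronger readings are tempting, and the documents support neither. A reader might infer that post-randomisation costs are not collected at all. Visit-linked and event costs are recoverable or named, and the unseen form may add more. A reader might also infer a built-in bias towards EmoLED. The protocol expects better healing in Group 2, and less informal care or lost work there would make m negative, so the omission would then count against EmoLED.

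**Conclusion.** The point holds as a scheduling gap in the secondary economic results. As written, routine between-visit resource use after randomisation is not systematically measured, although the societal cost comparison and the 16-week ICER depend on it. This is a missing schedule, not evidence that the data were never collected.

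Direction is unknown and size cannot be estimated from the documents. The figures of 3.1 and 1.6 points per visit-equivalent show scale only. They rest on an assumed cost base, full planned attendance and assumed values of d and m; at m = 0 there is no error. If Group 1 attends fewer than 32 visits, the denominator shrinks and each unit weighs more. The primary endpoint and the sample size are not affected.

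**What to change.** Keep the first-visit questionnaire as the baseline. Repeat the Economic section in both arms at the quality-of-life time points already planned (every 4 weeks and the last visit), with recall since the previous form. Add one item on dressing changes outside study visits: how many, by whom and with what product. Build each patient's 16-week cost from attended visits plus reported resources, and use that total in the Mann-Whitney test and the ICER. If a repeat was always intended, stating these time points in the Data Collection Form section closes most of the gap.

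Cost: four more short patient forms each (weeks 4, 8, 12 and 16), so at most 80 × 4 = 320. There will be fewer if observation ends early, plus the caregiver part where a caregiver is present. All fall at visits already planned, with no new procedure. The drawbacks are patient and caregiver time, some recall error over 4 weeks, and a cost result that may move in either direction.
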